6.6.8 Visual Analog Scale for Leg Pain Assessment

Right and left leg pain, as assessed by VAS (average pain over 24 hours), will be assessed at all visits, with the exception of Day 0. Right and left leg pain will be assessed separately. Though low back pain VAS scores will be used for efficacy assessments in this study, leg pain VAS scores will be used only for eligibility into the study and for safety assessments. A more detailed discussion of low back pain VAS assessment is provided in Section 6.7.2.

6.6.9 Laboratory Evaluations

Clinical laboratory tests will be performed according to the schedule indicated in Table 3. Specific laboratory parameters are displayed in Table 5.

Chemistry	Hematology	Special
Albumin	Hematocrit	hCG (urine)
Alkaline phosphatase (AP)	Hemoglobin	HIV
ALT (SGPT)	Red Blood Cells	anti-HLA class I and II antibody:
		Flow Class I and II % PRA
		(Specificity and DSA only for those
		Class I or II PRA results ≥5%)
AST (SGOT)	Platelets	hsCRP
CO2	White Blood Cells	Serum pregnancy test (beta hCG)
Blood urea nitrogen (BUN)	Neutrophils	
Calcium	Lymphocytes	
Chloride	Monocytes	
Creatinine	Eosinophils	
Direct Bilirubin	Basophils	
Total Bilirubin		
Glucose (non-fasting)		
Phosphorus		
Lactic dehydrogenase (LDH)		
Potassium		
Total Cholesterol		
Sodium		
Total protein		
GGT		
Uric Acid		

Table 5:	Laboratory Parameters

Any changes in clinical laboratory results deemed by the investigator to be clinically significant (see Section 7.5) or that qualifies as an adverse event should be documented.

All analyses, with the exception of urine pregnancy, will be performed at the central clinical laboratories.

Specificity testing and DSA results will be blinded until the end of the follow-up period.

6.7 Efficacy Assessments

Measurement of all efficacy parameters should be performed as described in Table 3. Standardized instructions for determining these parameters are provided in the following sections.

6.7.1 **Post-treatment Interventions Affecting the Treated Disc**

Post-treatment interventions over the 36-month post-treatment period are collected in this study for use in efficacy analyses as well as safety analyses. As these post-treatment interventions are used for all responder analyses, such interventions should be reported in a consistent manner. In order to maintain standardized classification of these interventions, a TEC will be used. (Section 12.2) provides greater detail regarding the TEC.

6.7.2 Visual Analog Scale for Low Back Pain Evaluation

Measuring pain intensity with a VAS is a useful and widely recognized tool in describing spine subjects. ⁶⁰ Pain intensity is recorded on a horizontal 100 mm VAS and measured as the distance in millimeters from the left origin of the horizontal VAS line and the point indicated by the subject as representing his/her level of pain.

A horizontal 100 mm visual analog scale (VAS) anchored on the left with the words "No Pain" and on the right with the words "Worst Possible Pain", will be used to measure low back, right and left leg pain intensity. Scores are obtained by measuring the distance in millimeters from the left origin of the line (0) to the point indicated with a slash placed by the subject to indicate the subject's level of pain.

During the course of this study low back pain (average pain over 24 hours and worst pain over 24 hours) will be measured using a 100 mm VAS at the following visits: screening, 1, 3, 6, 12, 18, 24 and 36 months post-treatment. This will be an assessment of average pain and worst pain

over the previous 24 hours (see Appendix 2). At screening, the VAS evaluation must be administered at least 2 weeks following any injections to relieve pain. Prior to administering the VAS, subjects will be instructed on its completion.

Subjects will be asked to complete the VAS directly on the corresponding worksheet completed during the in-clinic follow-up visits, which will serve as source documentation for this measurement. The in-clinic VAS assessments are considered the primary data source for VAS evaluations. However, the study source documents should reflect the date when each subject successfully completes the VAS or if there are any issues with VAS administration. The results of the VAS will be then transferred to the eCRF by the site using a validated method.

Under no circumstances should the worksheets containing the VAS be photocopied as photocopying may impact the length of the VAS line(s) and corresponding measurements.

Low back (average over past 24 hours and worst pain over 24 hours) and leg pain (average leg pain in left and right legs, individually over the past 24 hours) VAS evaluations will also be taken using e-diaries during the same 14 day period where pain medication usage is being collected. The VAS scores will be collected every day for the 14 day period with at least evaluations for 7 days. If more than 7 days of VAS scores are collected the last 7 days' scores will be used to calculate the average pain over a week.

Note: Low back and/or leg pain may generally be considered an adverse event and used in the evaluation of treatment safety. In this study, however, low back pain is also evaluated as an efficacy endpoint. Section 7.3 provides further details on how AEs of low back pain are defined.

6.7.3 Oswestry Disability Index

The ODI was first developed in 1976 as a specific outcomes tool for patients suffering from back pain. The validity, consistency and reproducibility of the ODI have been extensively tested and reviewed by Roland and Fairbank, 2000.⁶⁰ The questionnaire scores 10 aspects of the patient's home and work life and analgesic use. The disability index is then calculated as a percentage with a high percentage indicating a high level of disability. The ODI has been generally adopted since the mid-1980s to monitor the progress of patients suffering from back pain.

Improvements in functional mobility in this study will be based on the results of the ODI administered at screening, 1, 3, 6, 12, 18, 24 and 36 months post-treatment. Prior to

administering the ODI, subjects should be instructed on its completion. A qualified member of the clinic's staff should review the completed ODI to ensure that all questions have been covered and answered appropriately and that subjects use standard procedures for making corrections (see Appendix 3).

The questionnaire will be completed by the subject on the corresponding questionnaire forms at their in-clinic follow-up visit, which will serve as source documentation for this measurement. The in-clinic ODI assessment is considered the primary data source for ODI evaluations. The source documents should reflect the date when each questionnaire was successfully completed and any issues with its administration. The results of the questionnaire will be then transferred to the eCRF by the site.

An ODI evaluation will also be taken using e-diaries during the same 14 day period where pain medication usage is being collected. The ODI score must be taken at least once during the 14 day period. If more than one ODI score is collected, the most recent ODI score will be used.

6.7.4 Radiographic Evaluations

Plain radiographs and MR images will be used to assess the treated disc (see Appendix 1). All radiographic imaging will be sent to the imaging core lab for blinded, independent radiographic evaluation. Radiographic images will be assessed by two blinded and independent radiologists with a third reviewer to adjudicate any differences between the two reviewers.

Radiographic images will be made available to the investigator. Investigators should review these images, and any clinically significant findings, as well as the review itself, should be documented in the source.

During screening, the core imaging lab will assess the provided radiographic imaging (x-ray and MRI). The specified screening review assessments will be conducted by two blinded and independent radiologists with a third blinded and independent radiographic reviewer to adjudicate any differences between the two initial reviewers. The core lab will provide the investigator/site a report detailing the following:

- Modified Pfirrmann score at all lumbar levels
- Modic changes at all lumbar levels
- Absence or presence of disc protrusion, extrusion and/or sequestration at each lumbar level

- Absence or presence of spondylolisthesis/retrolisthesis of Grade 2 or more at each lumbar level
- Absence or presence of lumbar scoliosis of greater than a Cobb angle of 15 degrees in the lumbar spine.

The site will use the report provided by the core radiographic lab to determine whether the subject can be included in the study according to the inclusion/exclusion criteria (See Section 4.2)

MRI will be used specifically to assess change in the qualitative status of the intervertebral disc according to the Modified Pfirrmann scoring system. Each treated disc, as well as adjacent discs, will be evaluated for improvement from screening. The evaluation of modified Pfirrmann improvement will be made at screening and 12, 18, 24 and 36 months post-treatment. These evaluations will be performed by the core imaging provider. MRI will also be used for evaluation of the change in macromolecular content and hydration of the treated disc by using T1 rho and T2 mapping at facilities with this capability from baseline to 12, 18, 24 and 36 months post-treatment on a subset of subjects.

A/P and lateral X-rays of treated and adjacent levels will be collected at screening and 1, 3, 6, 12, 18, 24 and 36 months post-treatment. These images will be used to determine the height of the treated disc and any changes from baseline.

Flexion/extension X-rays will also be taken at screening and 1, 3, 6, 12, 18, 24 and 36 months post-treatment and will be used to determine spinal stability. The stability metric used in this study will be the QMA[®] Stability Index (abbreviated QSI, with units of standard deviations from mean). QSI is based on the translation per degree of rotation (abbreviated TPDR with units of % endplate width/degree) normalized per lumbar level. QSI is further defined in Appendix 1.

Radiographic evaluations may vary for a given subject depending on the time of day the assessments are made. Therefore, for each subject, all radiographic evaluations of a specific type (e.g., X-ray or MRI) should be taken at the same time of day at each assessment if possible, preferably in the morning.

For this study, the definition of a composite clinical stability success (CSS), relative to disc stability, is defined as QSI < 0 (determined by flexion and extension spine radiographs and indicating an improvement in disc stability compared to baseline) and at least a 50% reduction from baseline in low back pain VAS score (average pain over 24 hours) with no intervention at the treated level compared to baseline.

6.7.5 iPCQ, SAT, EQ5D, and Patient-reported Utilization Questionnaires

The iPCQ and EQ-5D questionnaires will be administered at each study visit: screening, 1, 3, 6, 12, 18, 24 and 36 months after treatment. The SAT will not be performed at screening, but at all post-treatment visits: 1, 3, 6, 12, 18, 24 and 36 months post-treatment. The Patient-reported Utilization Questionnaire will be administered at screening and 12, 18, 24 and 36 months.

iMTA Productivity and Cost Questionnaire (iPCQ)

The iPCQ is a measure of indirect costs arising outside the scope of the healthcare system, also known as productivity costs, that derive from health problems. The questionnaire consists of 3 modules focusing lost productivity due to absenteeism, presenteeism, and unpaid work (see Appendix 4).

Self-assessment of Treatment (SAT) Questionnaire

The SAT questionnaire is comprised of 5 items that assess subject-reported improvement and satisfaction with treatment (see Appendix 5).

EuroQoL EQ-5D

The EQ-5D is a standardized measure of health outcomes (see Appendix 6).

[figure not shown]
Patient-reported Utilization Questionnaire

[figure not shown]
This questionnaire is used as a tool for assessing direct healthcare costs related to back pain associated with DDD. The questionnaire requires subjects to provide a 12 month retrospective of relevant healthcare usage (see Appendix 7).

6.7.6 Post-Treatment Pain Medication Usage Collected by E-Diary

For collection of post-treatment pain medication use, subjects should be contacted by either IWRS or by the site, approximately 2 weeks prior to each post-treatment visit as a reminder to complete daily pain medication e-diaries for 2 weeks during the 30 days prior to each follow-up

visit other than for the 1 month visit that must be collected during the 14 days prior to the scheduled visit. At least 10 daily entries out of a possible 14 should be available at each study visit. Otherwise, absence of more than 4 entries will be considered a protocol deviation. Based on the opioid information entered into the e-diary during the 2 weeks prior to each post-treatment visit, it will be determined if subjects have shifted from baseline. Category shifts in opioid usage will be defined as:

CONFIDENTIAL

It is strongly recommended that there be no changes (increase or decrease) from or additions to baseline pain medications (opioids, NSAIDs, aniline analgesics, etc.) for at least the 24 month primary efficacy and safety follow-up period.

This is designed to minimize possible confounding treatment effects of alterations in pain medications. Furthermore, it is suggested that subjects do not schedule any medical procedures during the 2 weeks prior to any study visit which would require an adjustment in pain medications. However, should a significant increase in pain from baseline occur, the subject

CONFIDENTIAL

should be provided appropriate pain relief and an adverse event documented. Should there be any deviation from the baseline dose, information regarding the deviation must be documented.

7. SAFETY GUIDANCE

7.1 Definitions

7.1.1 Adverse Event

According to the International Conference of Harmonization [ICH] guideline for Good Clinical Practice, an AE is any untoward medical occurrence in a patient administered a pharmaceutical product and which does not necessarily have a causal relationship with this treatment. An AE can therefore be any of the following:

- Unfavorable and unintended sign (including an abnormal laboratory finding), symptom, or disease temporally associated with the use of a medicinal (investigational) product, whether or not considered related to the medicinal (investigational) product.
- Any new disease or exacerbation of an existing disease (a worsening in the character, frequency, or severity of a known condition)
- Recurrence of an intermittent medical condition (e.g., headache) not present at baseline
- Any deterioration or abnormality in a laboratory value or other clinical test (e.g., ECG, X-ray) that is associated with symptoms or leads to a change in study treatment or concomitant treatment or discontinuation from study drug
- Adverse events that are related to a protocol-mandated intervention, including those that occur prior to assignment of study treatment (e.g., screening procedures such as biopsies etc.).

Adverse events will be captured following signing of the informed consent form. Pre-existing conditions (i.e., medical history) which **worsen** during a study are to be reported as AEs.

7.1.2 Serious Adverse Event (Reportable to the Sponsor within 24 Hours)

An SAE is any adverse event that meets any of the following criteria:

- Fatal (i.e., the adverse event actually causes or leads to death)
- Life threatening (i.e., the adverse event, in the view of the investigator, places the subject at immediate risk of death). This does not include any adverse event that had it occurred in a more severe form or was allowed to continue might have caused death
- Requires or prolongs inpatient hospitalization

- Results in persistent or significant disability/incapacity (i.e., the adverse event results in substantial disruption of the subject's ability to conduct normal life functions)
- Congenital anomaly/birth defect in a neonate/infant born to a mother exposed to investigational product
- Significant medical event in the investigator's judgment (e.g., may jeopardize the subject or may require medical/surgical intervention to prevent one of the outcomes listed above).

Any AE that is defined as serious and which occurs during the course of the study, regardless of the treatment arm must be reported within 24 hours of the investigator becoming aware of the event.

7.1.3 Severity

A clinical determination will be made of the severity of an AE. The terms "severe" and "serious" are not synonymous. Severity is a description of the intensity of the manifestation of the AE and is distinct from seriousness, which implies a subject outcome. Severity will be assessed according the following scale:

Mild	Discomfort noticed but no disruption of normal daily activity
Moderate	Discomfort sufficient to reduce or affect daily activity
Severe	Inability to work or perform normal daily activity

7.2 Relationship of Adverse Event to Study Treatment or Study Procedure

A determination will be made of the relationship between an AE and the treatment received. A causal relationship is present if a determination is made that there is a *reasonable possibility* that the AE may have been caused by the study treatment and/or study procedure. In general, a causal relationship will be assigned when evidence exists to support the causal relationship. When assessing a potential relationship between the study treatment and/or study procedure and an AE, the following parameters should be considered:

- Temporal relationship between study treatment and/or protocol-specified procedures and the AE
- The biological plausibility that the study treatment and/or procedure caused the event
- Any underlying/concurrent illness in the subject
- Concomitant medications the subject may have received

• How commonly the event occurs in the study analysis set independent of treatment.

Examples of evidence to suggest a causal relationship between the study treatment and/or study procedure and the AE include the following:

- A single occurrence of an event that is uncommon and known to be strongly associated with investigational product exposure or study procedure (e.g., angioedema, discitis, hepatic injury, Stevens-Johnson Syndrome).
- One or more occurrences of an event that is not commonly associated with investigational product exposure or study procedure, but is otherwise uncommon in the analysis set exposed to the drug (e.g., tendon rupture).

Low back pain within 14 days of the treatment procedure is expected.

7.3 Adverse Events of Special Interest – Back Pain

Low back pain may generally be considered an adverse event and used in the evaluation of treatment safety. In this study, however, low back pain is also evaluated as an efficacy endpoint. Pain data provided on the low back pain VAS will not routinely be considered an adverse event in this study. If a subject reports an adverse event of low back pain, the following information will be collected from the subject:

- 1. Whether or not the pain is of increased intensity from baseline
- 2. Whether or not there is an increased frequency of pain, regardless of intensity, as compared to baseline
- 3. Whether or not the pain is in a different location in the lower back as compared to baseline
- 4. Whether the symptoms required an unscheduled visit
- 5. The subject's assessment of the cause of the event, if any specific cause is suspected.

A back pain AE should be reported if the subject answers yes to questions 1-4 above. If a back pain AE is reported, the subject's assessment of the cause of the event should also be recorded if any specific cause is suspected.

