6.4.6 Determination of Baseline SI Joint Pain

A targeted physical examination to rule out SI joint pain will be performed at screening. Clinical examination of the subject's lumbar spine and pelvis should be performed. As part of this examination, the following Laslett's Tests⁵⁹ should be performed.

Test	Description (Positive Findings)					
Distraction	Patient supine. Examiner applies posterolateral directed					
Distraction	pressure to bilateral ASIS. (Reproduction of pain)					
	Patient side-lying. Examiner compresses pelvis with					
Compression	pressure applied over the iliac crest directed at the					
	opposite iliac crest. (Reproduction of symptoms)					
Thigh Thrust	Patient supine. Examiner place hip in 90 deg flexion and					
	adduction. Examiner then applies posteriorly directed					
	force through the femur at varying angles of					
	abduction/adduction. (Reproduction of buttock pain)					
Sacral Thrust	Patient prone. Examiner delivers an anteriorly directed					
Sacial Illust	thrust over the sacrum. (Reproduction of pain)					
Gaenslen's	Patient supine with both legs extended. The test leg is					
	passively brought into full knee flexion, while the					
	opposite hip remains in extension. Overpressure is then					
	applied to the flexed extremity. (Reproduction of pain)					

Table 4: Physical Examination for Evaluation of SI Joint Pain

Subjects who present with all of the following symptoms should be considered positive for SI joint pain:

- 1. Maximal tenderness at or below L5,
- 2. Tenderness over the posterior superior iliac spine / sacral sulcus, and
- 3. Three positive SI joint provocation tests (Laslett's tests).

Should the results of the targeted examination prove inconclusive, the investigator may perform a diagnostic injection of anesthetic to the SI joint in order to determine presence of SI join pain.

6.4.7 **Pregnancy Tests**

A serum pregnancy test will be analyzed for all females of childbearing potential at screening. Women of childbearing potential are defined as premenopausal and not surgically sterilized or postmenopausal for fewer than 2 years. A urine pregnancy test will be performed prior to administration of study treatment to confirm a negative result. If the urine pregnancy test is positive, study drug will not be administered that day, and the result will be confirmed by a serum pregnancy test.

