7.5 Laboratory Test Abnormalities

Laboratory test results will appear on electronically produced laboratory reports directly from the central laboratory. Local laboratory results should be recorded on the eCRF, if applicable.

Any laboratory result fulfilling the criteria for an AE or SAE should be recorded on the eCRF and reported to the designated responsible parties in safety accordingly. The preference is to report a diagnosis rather than the laboratory value as the adverse event. However, if a diagnosis has not been confirmed, a clinically significant laboratory value should be reported including a modifier (e.g., worsening, increased, decreased) until a final diagnosis can be reported.

Any treatment-emergent clinically significant abnormal laboratory result is defined as meeting one or more of the following conditions:

- Accompanied by clinical symptoms
- Requiring a change in concomitant therapy (e.g., addition of, interruption of, discontinuation of, or any other change in a concomitant medication, therapy or treatment).

This applies to any protocol and non-protocol specified safety and efficacy laboratory result from tests performed after informed consent form signature, which fall outside the laboratory reference range and are considered clinically significant by the investigator. This does not apply to any abnormal laboratory result which falls outside the laboratory reference range but which does not meet the criteria for clinical significance (these will be analyzed and reported as laboratory abnormalities).

In the event of clinically significant abnormal laboratory test values, the tests should be repeated and followed up until they have returned to the normal range and/or an adequate explanation of the abnormality is found. If a clear explanation is established, it should be recorded on the eCRF.

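### Section 7.3 does not say whether any or all of four yes answers make a back pain AE reportable; read as all four, it clashes with 7.1.1 and 6.7.6 and would under-record the named AESI

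*Combined protocol and SAP*

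**What the plan says.** Section 7.3 begins with a subject who has already complained: "If a subject reports an adverse event of low back pain, the following information will be collected from the subject". Five items follow. The first asks whether pain is more intense than at baseline. The second is "Whether or not there is an increased frequency of pain, regardless of intensity, as compared to baseline". The third is "Whether or not the pain is in a different location in the lower back as compared to baseline". The fourth is "Whether the symptoms required an unscheduled visit". The fifth asks what the subject thinks caused the event. The reporting rule is then: "A back pain AE should be reported if the subject answers yes to questions 1-4 above".

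Section 6.7.2 sends the reader to 7.3 for how low back pain AEs are defined. Section 9.7.1 places AEs of worsening low back pain inside the primary safety endpoint. It plans summaries through 24 months by arm, severity and time since injection, and by responder status on the primary efficacy endpoint for events from 3 to 24 months.

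**The concern.** The rule has no logical operator, and its literal sense is that all four answers must be yes. On that sense, a subject whose usual pain becomes much worse in its usual place answers no to the third question and falls outside the rule. So does a subject whose worsening is handled without an unscheduled visit.

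These are ordinary forms of worsening low back pain, which is what the AESI is meant to capture. If sites applied 7.3 in this way, the AESI count would be too low. With up to 45 sites (section 3.3), some could apply all four and others any one, and the reported rate would then mix two definitions.

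**Working it through.** The plan states no rate, sample size or error level that depends on this rule, so there is no figure to reproduce. The check is a comparison of passages.

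**1. Does the protocol state its operator elsewhere?** Yes.
- Section 6.4.6, SI joint pain: "Subjects who present with all of the following symptoms should be considered positive".
- Section 7.1.2, serious events: "An SAE is any adverse event that meets any of the following criteria".
- Section 7.5, laboratory abnormalities: "is defined as meeting one or more of the following conditions".

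Section 7.3 gives no such word.

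**2. What do the other sections make reportable?**
- Section 7.1.1 counts worsening of a known condition in its character, how often it occurs or how severe it is. One of the three is enough. It also requires worsened pre-existing conditions to be reported.
- Section 6.7.6 has an AE documented when pain rises significantly from baseline. It sets no condition on location or type of visit.
- Section 6.6.4 has adverse changes since baseline noted as AEs at follow-up examinations.

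**3. Cases side by side.**

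| Complaint | 7.1.1 | 6.7.6 | 7.3 as all four | 7.3 as any |
|---|---|---|---|---|
| More intense, usual location, unscheduled visit | AE | AE if significant | not reported | reported |
| More frequent, same intensity, usual location, no unscheduled visit | AE | silent | not reported | reported |
| More intense, more frequent, new location, no unscheduled visit | AE | AE if significant | not reported | reported |
| New location only | AE only if location counts as character | silent | not reported | reported |
| Unscheduled visit only | not named | silent | not reported | reported |
| All four yes | AE | AE if significant | reported | reported |

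In the first three rows, the all-four reading departs from 7.1.1, and in the first and third also from 6.7.6 when the increase is significant. Rows four and five show that 7.1.1 does not settle whether a new location alone or an unscheduled visit alone should count.

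**4. Direction and size.** Every report with four yes answers also has at least one, so the all-four count cannot exceed the any count. They are equal only if every report has four yes answers. The gap depends on how often each answer is yes, which the documents do not give.

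To show how open the size is, assume independent answers with a common yes-probability p. This assumption is not in the documents and is unlikely to hold. The share of any-rule reports kept by the all-four rule is p⁴ / [1 − (1 − p)⁴]:
- p = 0.3: 0.0081 / 0.7599 = 1.1%
- p = 0.5: 0.0625 / 0.9375 = 6.7%
- p = 0.7: 0.2401 / 0.9919 = 24.2%
- p = 0.9: 0.6561 / 0.9999 = 65.6%

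This range is too wide to estimate the loss in this trial. It shows the direction only.

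**The case against.** The strongest reply is that 7.3 says *if*, not *only if*. Even as all four, it can be a sufficient condition that leaves the general duties in 7.1.1 and 6.7.6 in force. That stands: the under-count needs the all-four reading and also its use as the exclusive rule. But section 6.7.2 presents 7.3 as the place where these events are defined, which invites exclusive use.

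The second reply is that the authors probably meant any. The second question counts increased frequency whatever the intensity, and that clause does nothing if increased intensity is also required. Section 9.7.1 plans to summarize subjects with at least a 50% VAS reduction at the time of a back pain AE, and few could exist if increased intensity were mandatory. Both cues are sound, though neither contradicts all four outright. They support correcting the sentence; they do not tell a site how to apply it.

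Third, the detailed SAP text and eCRF instructions are not visible and could state the rule. That is possible, and it limits what can be said about site practice. It would not mend the protocol sentence.

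A reader might also infer that events in the first 7 days are especially at risk, because the first scheduled visit after Day 0 is at 1 month. The documents do not show this. AEs are recorded before discharge on Day 0, early events can be elicited at the 1-month AE evaluation, and the absence of a scheduled visit does not mean that no unscheduled one was needed.

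**Conclusion.** The concern holds in a limited form. As printed, the rule is ambiguous, and its literal reading is inconsistent with the protocol's own AE definition. Sites that apply all four as the exclusive rule would under-record worsening low back pain, and sites could differ in which rule they apply. The conclusion rests on two conditions: that a site reads the sentence as all four, and that it treats 7.3 as the whole definition.

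Three stronger inferences are not supported:
- That the trial does under-count these events. The answers and actual site practice are not in the documents.
- That the ambiguity favors an arm. The wording is common to all arms and randomization is stratified by site (section 9.2), so mixed site practice would not by itself do so.
- That serious events or efficacy are affected. SAEs are reported regardless under section 8.1, and VAS, ODI and adjudicated interventions do not pass through this rule.

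The loss would fall mainly on non-serious events in a descriptive summary. It is still worth correcting, because this is the only AESI named in the visible text and the correction is cheap.

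**What to change.** Reconcile 7.3 with 7.1.1 and 6.7.6 by stating the operator. A yes to any one listed change that meets the protocol's own AE definition should be enough to report; this covers at least increased intensity or increased frequency. State separately whether a new location alone, or an unscheduled visit alone, qualifies, since 7.1.1 does not decide either. Add a cross-reference from 6.7.6 to 7.3.

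Keep the individual answers on the eCRF for every subject report of back pain, so that counts under either reading can be tabulated. Section 7.3 collects the answers before the rule is applied, but earlier reports can be re-derived only where those answers were kept.

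The cost is a one-sentence amendment, one cross-reference and a short notice to sites. The downside is that more non-serious back pain AEs will be recorded in all arms.
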